Another novel aspect of this project will be the evaluation of baseline pain sensitivity, measured with field-based techniques, as a potential predictor of response to the interventions. Some patients with cLBP have a lower threshold for pain, due to an augmented central pain processing mechanism. As such, measures of pain sensitivity may prove useful in understanding an ongoing refractory pain-process; it is possible that patients who have a lower threshold for pain may respond differentially to behavioral interventions. In particular, these patients may experience greater improvement when CBT-P is offered as an additional program component (compared to PA alone), since these cognitive skills have been shown to influence pain processing. This pilot study will be an important step, ultimately leading to guidance regarding whether some older adults with cLBP should be offered a PA only vs. PA + CBT-P.

To our knowledge this will be the first study to examine the home-based PA only and PA + CBT-P programs among older adults with cLBP, as well as the first to evaluate central pain sensitivity as a predictor of response to these interventions. Therefore preliminary data are needed to support a larger project. Our specific aims are:

**Specific Aim 1:** Examine the feasibility of conducting 12-week home-based, telephone-supported programs of: 1.) PA only and 2.) Combined PA+CBT-P, among older veterans (65+ years) with cLBP. Quantitative measures of feasibility will include the proportions of patients who initiate and complete the programs and adherence to in-home PA recommendations and cognitive behavioral skills practice. We will also collect in-depth qualitative information to assess aspects of the interventions that may need to be modified prior to a larger study.

**Specific Aim 2:** Collect preliminary data to evaluate the efficacy of the PA only and PA + CBT-P programs among older veterans with cLBP. Main outcomes will be an objective test of general physical function (timed up-and-go (TUG)) and self-reported physical function (PROMIS Health Assessment Questionnaire (PROMIS-HAQ)). Secondary outcomes will include: Patient Specific Functional Scale (PSFS), Satisfaction with Physical Function Scale, LBP-specific disability (Roland-Morris Low Back Pain and Disability Questionnaire (R-MDQ)), and the Coping Strategies Questionnaire.

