**Specific Aim 3:** Examine whether baseline distal Pressure-Pain Threshold, an established biological marker of pain sensitization, and the Central Sensitivity Inventory, which measures health-related symptoms common to central pain sensitization, predict differential response to the PA only and / or PA + CBT-P programs among older veterans with cLBP.

There is a need to develop and disseminate effective programs to improve PA and ultimately physical function in this patient subgroup. This project will be a key first step in evaluating a home-based PA and PA + CBT-P programs that could be widely disseminated in the VA at relatively low cost and reach many functionally vulnerable older veterans with cLBP.

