**Analyses**: We will compare outcomes across study groups with analysis of covariance (ANCOVA) models (or non-parametric alternatives such as the Kruskal-Wallis test, when indicated), controlling for baseline values. Since this is a pilot study with small sample size, even clinically relevant differences may not be reflected as statistically significant differences (e.g. p<0.05). Therefore we will focus on effect sizes for the two intervention groups and evaluation of whether between-group difference reflects a threshold of clinical relevance. These data, along with means and standard deviations of baseline scores, correlations between baseline and follow-up scores, and attrition rate will also be used to calculate the appropriate sample size for a larger clinical trial. To address Aim 3, we will first plot baseline PPT and CSI values vs. changes in outcomes for each intervention group; we will also calculate correlations for these same associations. This will allow us to evaluate whether associations between baseline pain sensitivity measures and changes in outcomes may differ between the two intervention groups. Based on our previous experience with analyzing PPT data, we will also dichotomize these baseline scores at a <4kg vs. >=4kg to represent low and high pain sensitivity. We will then add an interaction term to our ANCOVA models (study group \* dichotomous PPT variable) to evaluate whether intervention effects vary by this indicator. If a significant interaction term is found, we will stratify the sample by this variable and explore the nature of the interaction. A similar analysis will be conducted with the established cutpoint on CSI scale or 40 out of 100.

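### Aim 3 commits to exploring the group-by-pain-sensitivity interaction only if it is significant, so a pilot of 20 per arm may report no category-specific estimates; one added sentence would settle it

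*Combined protocol and SAP*

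**What the plan says.** All of this is in the Analyses paragraph of Research Design and Methods, unless another place is named.

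- **General stance.** Because the pilot is small, "even clinically relevant differences may not be reflected as statistically significant differences (e.g. p<0.05"; the plan continues: "Therefore we will focus on effect sizes for the two intervention groups". This is written about the comparison of outcomes across study groups.
- **Aim 3, first step, unconditional.** Baseline PPT and CSI are plotted against, and correlated with, change in outcome in each intervention group. The stated purpose: "This will allow us to evaluate whether associations between baseline pain sensitivity measures and changes in outcomes may differ between the two intervention groups".
- **Aim 3, second step, unconditional.** "We will then add an interaction term to our ANCOVA models", with PPT cut at 4 kg. For CSI: "A similar analysis will be conducted with the established cutpoint on CSI scale or 40 out of 100".
- **Aim 3, third step, conditional.** "If a significant interaction term is found, we will stratify the sample by this variable and explore the nature of the interaction". No alpha is given for this test.

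Specific Aim 3 asks whether the baseline measures "predict differential response to the PA only and / or PA + CBT-P programs among older veterans with cLBP". Specific Aims gives the reason for the pilot: "Therefore preliminary data are needed to support a larger project".

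**The concern.** The plan sets p-values aside for the group comparison, where power is better, and then relies on one for the interaction, where power is worse. The caution about p<0.05 was written for the main comparison, but it applies with more force here.

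Specific Aims presents the study as a step towards knowing whether some patients should be offered PA alone and others PA + CBT-P. The quantity closest to that question is the PA + CBT-P versus PA difference within each sensitivity category. If the follow-up is done only after a significant interaction, two things happen. Most pilots of this size would carry no commitment to show that difference. Where it is shown, it has been selected for being large, which makes it a poor guide for the larger project.

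The stake is limited. The sample-size inputs listed in the Analyses paragraph do not include subgroup estimates, and the main comparisons are untouched.

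**Working it through.** The documents give no power, SD, target effect or derivation of the sample size, so there is no stated figure to reproduce. What follows shows how strongly the condition acts.

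**Inputs from the documents.** 60 participants, equal allocation to three arms (Study Design): 60/3 = 20 per arm. ANCOVA adjusted for baseline, with a three-group by two-category interaction (Analyses).

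**Assumptions, because the documents give no value.** Alpha 0.05 or 0.10. Interaction of 0.5, 0.8 or 1.0 residual SD, present in the PA + CBT-P arm only. Per-arm split of the moderator (a in one category, b in the other) of 10/10 or 6/14. With 20% loss (16 per arm), 8/8 or 5/11.

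**Step 1: standard errors, in residual SD.**
- Main PA + CBT-P versus PA contrast: √(2/20) = 0.316.
- Interaction for the same pair of arms: √(2(1/a + 1/b)). At 10/10 this is √(2 × 0.2) = 0.632, a ratio of 2.0. The other splits give 0.690 (6/14), 0.707 (8/8) and 0.763 (5/11).

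**Step 2: chance that the condition is met.** Two-df interaction F test, error df N − 7, noncentrality (2/3)d²/(1/a + 1/b). For d = 0.8 at 10/10 the noncentrality is (2/3)(0.64)/0.2 = 2.13.

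| Per-arm split | alpha 0.05: d = 0.5 / 0.8 / 1.0 | alpha 0.10: d = 0.5 / 0.8 / 1.0 |
|---|---|---|
| 10/10 | 11 / 23 / 34% | 19 / 34 / 46% |
| 6/14 | 10 / 20 / 29% | 18 / 30 / 41% |
| 8/8 | 10 / 19 / 27% | 17 / 29 / 39% |
| 5/11 | 9 / 17 / 24% | 16 / 26 / 35% |

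A 1-df test of the PA + CBT-P versus PA interaction (10/10, alpha 0.05) gives 12 / 24 / 34%. A main PA + CBT-P versus PA difference of the same size has 34 / 70 / 87%.

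**Step 3: where the condition is met more often.** Residual SD is √(1 − r²) outcome SD, where r is the baseline to follow-up correlation. An interaction of 1.0 outcome SD is therefore 1/√(1 − 0.36) = 1.25 residual SD at r = 0.6 and 1/√(1 − 0.49) = 1.40 at r = 0.7. Over the four splits, power is then 35 to 60% at 0.05 and 48 to 72% at 0.10.

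**Step 4: size of the estimates that pass.** Simulation of the ANCOVA, 20,000 runs per scenario, keeping runs with a significant 2-df test at 0.05, 10/10 split. True interactions of 0.5 / 0.8 / 1.0 gave mean estimates of 1.24 / 1.44 / 1.55. Repeat runs gave 1.21 to 1.27 for a true 0.5. At alpha 0.10 the means were 1.10 / 1.32 / 1.43. Over all runs, without selection, the estimates are unbiased.

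**Step 5: precision if always reported.** The 95% half-width for a between-arm difference within a category, from the interaction model, is t(N − 7) × √(2/n). At n = 10 per cell it is 2.006 × 0.447 = 0.90 residual SD. At n = 6 it is 1.16, at n = 14 it is 0.76, and at n = 5 with 16 per arm it is 1.28. A separate stratified fit gives 0.92 (26 df) at n = 10 and 1.39 (11 df) at n = 5, so stratifying adds no precision to the model already planned.

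**The case against.** A reader might infer that the plan forbids reporting category-specific results unless the interaction is significant. The text does not say that. It makes a follow-up analysis conditional, and the interaction model, from which those differences can be read at any p-value, is fitted regardless. What stands is narrower: the plan does not commit to showing them either.

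A reader might also infer that Aim 3 rests wholly on a significance test. It does not. The plots and correlations are unconditional, use the continuous scores, and are meant to compare the two intervention groups. They answer Aim 3 informally, but they supply no adjusted between-arm difference and no interval in either category.

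The best defence is that following up subgroups only after a significant interaction is a conventional guard against over-reading them, and can sit beside a focus on effect sizes for main effects. That is fair. As a guard it is imperfect here, because what passes is inflated and what fails may be taken as absence of modification.

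The percentages are per test and depend on the assumptions. With two moderators and two primary outcomes there are at least four tests, so some condition will be met more often than the table shows. Even with no interaction at all, four independent tests at 0.05 would give 1 − 0.95⁴ = 18.5%.

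Finally, always-reported intervals will often not separate benefit from harm. That limits the gain but does not remove it.

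**Conclusion.** The point holds as a minor improvement to an exploratory aim. The plan fits the interaction unconditionally, commits to exploring it only on significance at an unstated level, and makes no other commitment to category-specific between-group estimates. For assumed interactions of 0.5 to 1.0 residual SD in one arm, a single test at 0.05 meets the condition in roughly 10 to 35% of trials. This rises under larger effects, a looser alpha or several tests, so it would be wrong to say that the condition is never met. Estimates that meet it are exaggerated, by more than a factor of two when the true value is 0.5. The twofold standard error at an even split follows from the design; the power and exaggeration figures rest on the stated assumptions. The documents do not support a claim that the main comparisons or the planning of the larger trial are compromised.

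**What to change.** Keep the conditional sentence for any further stratified exploration, including of secondary outcomes, and add:

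> *For the two primary outcomes, the interaction estimates and the category-specific between-group differences (PA + CBT-P vs PA, and each program vs wait list) from the interaction ANCOVA (PPT 4 kg, CSI 40) will be reported with 95% CIs whatever the interaction p-value, and interpreted as exploratory.*

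Adding to the sentence, not replacing it, preserves follow-up of secondary outcomes. Naming all three contrasts matches an aim that covers either program.

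The cost is one sentence and one table, with no change to design, data collection or fitted models. The downside is wide intervals: about 0.9 residual SD either side per category at 10 per cell, and up to about 1.3 with an uneven split and 20% loss. There is also some risk that subgroups are over-read, which the exploratory label and the restriction to two outcomes limit but do not remove.

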### **Privacy and Confidentiality and Information Security**

The following measures will be taken to protect participants' privacy / confidentiality:

- The study involves sending recruitment letters; these will not contain the name of the study or any reference to the condition being studied.
- When leaving telephone messages regarding study activities, team members will not leave information about the study or condition, just the name of the study team member calling from the Durham VAMC.
- This study involves telephone calls to administer a screening interview and conduct parts of the intervention. These will be conducted in a manner that minimizes the possibility that any person not associated with the study can hear the participant's name or any other identifiable information.
- The study involves in-person consent, interviews, and physical function assessments. The consent process and interviews will be conducted in a private room in the VA. Some physical function assessments may need to be conducted in an appropriate area, such as a VA physical therapy clinic that has a therapy mat. For these assessments, we will use a private therapy room if available; if unavailable we will minimize interactions with non-study personnel and not verbally utilize any

identifiable information in the interaction. We will also let the participant know that they may choose not to participate in those assessments and still continue in the study.

- Use of paper documents will be minimized, and all of these documents (e.g., consent forms) will be stored in a locked file cabinet in the office of a study team member located on the 6th floor of the NC Mutual Building.
- All electronic study data will be stored on a secure VA server accessible only to study team members.

## Information Security

The following addresses practices related to information security:

- The study requires use of some individually identifiable data, including participant names, street address, city, county, zip code, telephone number, and Social Security number to complete telephone screening, send recruitment letters, and appointment reminder letters. We will collect the minimum amount of study data required to complete study aims involving recruitment, outcome assessment and reimbursement. These data will be stored in the study tracking database (\vhadurhsrfile1\ Distributed Apps\HSRDTTrackingApp). This database will also be used to keep track of study related telephone calls to participants, opt-out calls, study payment dates, and study appointments.
- Some data will be collected prior to consent, as outlined in our HIPAA waiver request, and on page 4 "Participants and Recruitment" above. We will collect the minimum amount of data to be able to identify potentially eligible patients and contact them about the study. These data will come from VA medical records (see section above on Participants and Recruitment), as well as a brief telephone-based screening questionnaire to capture information not reliably included in the medical record.
- For patients who enroll in the study, other information will be collected via questionnaires (and results of functional tests), completed in person at the VA.
- Screening and outcome measures will be recorded using DatStat Illume™, provided per VA enterprise license and funded by HSR&D. Illume is a web-based survey tool. Data will be stored on a secure VA server. However, we will have consent forms and a form on which we will record results of functional tests (the latter will not include PHI; study ID only). All hard copies of data will be stored in a locked filing cabinet in the office of a study team member located on the 6th floor of the NC Mutual Building. All electronic data will be stored on a secure VA server (\vhadurshrdfile1\\$projects\PACe\_LBP), managed by Durham VA HSR&D personnel, in a folder accessible only to study team members on the IRB approved staff listing.
- Consent forms with patient names will be transported from the VA interview rooms to the study team's offices in Legacy Tower by an approved study team member; these documents will remain in direct possession of the study team member in a locked courier bag throughout transport. VA clinicians may refer patients to the study team, with patients' permission; this will be via a consult option within the medical record.
- Only individuals on the IRB approved staff listing will have access to study data. This will be housed on a VA secure server, with folder access given by HSR&D IT personnel only to individuals on the staff listing. Access to the study data will be removed for staff members that are no longer part of the study team.
- [name] is a co-investigator from Duke. He will obtain a VA WOC appointment (and complete human subjects training) and VA credentialing prior to any study involvement. His human subjects' activities on this project will all be confined to the VA; no clinical involvement will take place at Duke.
- We will share a de-identified data set with study investigators at Duke for the purpose of conducting some secondary data analyses at that site. This data will contain no elements of PHI per the HIPAA list, and there will be no ID provided to Duke OR retained by the VA that would allow re-linkage of the Duke data set back to any personal health information in the VA data set. The data will be transferred to Duke using an encrypted CD, encrypted thumb drive or other VA approved method, and stored on a secured, password protected server in the Department of Orthopedic Surgery at Duke where [name] has his primary appointment. The data will be accessible only to study personnel on the Duke IRB study staff listing.
- Information will be accounted for by regular checks and reports generated from the tracking database (e.g., information on participant stages within the study); this will be approximately biweekly. In addition the study team will maintain a check sheet associated with tasks and data collected for the baseline

and follow up assessments; this will help to ensure that all required tasks are completed (e.g., providing participant with copy of the signed consent form) and that all data collected and stored will be in accordance with the VA records control schedule.

- Security measures to protect individually identifiable data will include storage of electronic data only on a VA secure server and storage of paper documents only in locked filing cabinets in study team offices.

Any suspected or confirmed security or privacy incident will be reported to the Information Security Officer and Privacy Officer immediately. Once study data are no longer needed, paper files will be shredded in accordance with VA records control requirements for destruction of sensitive information. Information in electronic format will be deleted or purged from data files in accordance with VA records control requirements. AND: Should any incident such as theft or loss of data, unauthorized access of sensitive data or non-compliance with security controls occur it will be immediately reported according to VA policy. All incidents regarding information security/privacy incidents will be reported to the ISO and PO within 1 hour of acknowledgement of issue and done so using the VHADUR Research Events Report e-mail group ([contact]).

**Participant Safety and Quality Control:** The physical therapist and exercise counselor will follow all VA patient safety standards. Because of the variable and exacerbating / remitting nature of chronic LBP, we expect that some participants may experience increases (or decreases) in their pain during the course of the study, regardless of treatment group. Drs. [name] and [name] will train the exercise counselor in delivering the PA and CBT-P programs. The exercise counselor will perform practice calls with study team members, with feedback provided by Drs. [name] and [name]. In addition, a subset of intervention telephone calls will be audio recorded (approximately the first ten of these sessions and 10% of calls thereafter) and Drs. [name] and [name] will listen to these to ensure adherence to the intervention protocol. When these telephone calls are audio recorded, the participant will be notified verbally, and the consent form will also notify participants that these calls may be recorded. The audio recordings for fidelity checks of intervention calls will be digitally recorded using a VA approved USB recorder, currently a Sparky device. The recordings are made directly to a VA server (\vhadurshrdfile1.v06.med.va.gov\\$projects\PACe\_LBP) and are only accessible to study team members. [name] will train the research assistant to administer the PPT measurement, following an a priori protocol; reliability of the PPT measurement will be established through practice trials prior to enrollment of participants. Brief training in PPT measurement has been shown to produce highly reliable results in trained observers. In the event of any adverse events, [name] will provide consultation regarding whether it is appropriate for the participant to remain involved in the study.

